#### 2.3.1 Primary Objectives

- Safety: To estimate and compare (each vaccine group to placebo) the frequency and severity of adverse events (AEs) following study product administration (Day 0) through Day 56
- Immunogenicity: To estimate and compare (between the vaccine groups and to the benchmark of 70%) the percentage of vaccinees having a ≥4-fold rise in serum RSV-neutralizing antibodies at the Day 56 Visit

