#### 3 **Outcome Measures**

#### 3.1 **Primary Outcome Measures**

Safety Outcome measures:

- Grade 1 or higher solicited AEs as defined in Appendix 1 from Day 0 through Day 28
- Grade 2 or higher LRIs as defined in Appendix 1 from Day 0 through Day 28
- Serious AEs as defined in Appendix 4 from Day 0 through Day 56

Additional grading criteria are included in Appendix 2 and 3.

Immunogenicity Outcome measure:

≥4-fold rise in serum RSV-neutralizing antibody titer from pre-study product administration (screening) to the Day 56 Visit

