#### 4.2 Analysis Approaches (Primary Objectives)

#### 4.2.1 Analysis of the primary safety objective

There are three primary safety outcome measures (Section 3.1). For each, the number and proportion of participants experiencing at least one primary safety outcome measure in the identified time frames will be summarized by arm with 95% exact confidence intervals (CIs) using the Clopper-Pearson method. Proportions in each vaccine group will be compared to the placebo group using two-tailed Fisher's exact tests with a nominal significance level of 0.05. Differences in proportions between each vaccine arm and the placebo arm will be summarized with 95% CIs.

To account for potential ascertainment differences related to COVID-19, differences in proportions between each vaccine arm and the placebo will be summarized by calendar year of enrollment. A Breslow-Day test with a nominal significance level of 0.05 will be used to test for homogeneity in the vaccine effect by calendar year for each comparison between arms. Unless the Breslow-Day test indicates there is not homogeneity in vaccine effect by calendar year, a strata-adjusted difference in proportions will be summarized using a Cochran-Mantel-Haenszel method with 95% Klingenberg (2014) confidence limits.

In addition, for each primary safety outcome measure, the worst (highest) grade experienced by each participant will be summarized. The severity of solicited AEs from Days 0-28, unsolicited AEs from Days 0-28, and serious AEs from Days 0-56 will be summarized by category and by MedDRA Preferred Term (PT). The worst (highest) adverse event grade within each PT is counted for each participant. Rare events (LRIs and serious AEs) will be listed with details including site-assessed relationship with the study product.

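### For fever, otitis media and upper respiratory illness that is not serious, severity above Grade 1 is tabulated but not compared with placebo, although the primary safety objective is to compare severity

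*SAP*

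**What the plan says.** SAP Section 2.3.1 words the primary safety objective as "To estimate and compare (each vaccine group to placebo) the frequency and severity of adverse events (AEs", and the period covered ends at Day 56. Severity is part of what is to be compared.

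Section 3.1 turns this into three outcome measures. The broadest is "Grade 1 or higher solicited AEs as defined in Appendix 1 from Day 0 through Day 28". The second restricts attention to LRIs and raises the cut to Grade 2, over the same 28 days. The third counts serious events, with a longer window that closes at Day 56.

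Section 4.2.1 reduces each to the proportion of participants with at least one such event. "Proportions in each vaccine group will be compared to the placebo group using two-tailed Fisher's exact tests" at a nominal 0.05 level, and the differences from placebo are given with 95% confidence intervals. There is also a summary by calendar year of enrollment, with a year-adjusted difference unless the homogeneity test indicates otherwise.

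On grade, the same section says that "for each primary safety outcome measure, the worst (highest) grade experienced by each participant will be summarized". It also plans to summarize severity by category and by MedDRA Preferred Term. It names no between-arm difference, interval or test for grade.

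**The concern.** The verb in the objective is stronger than the analysis for part of the outcome. The solicited-event outcome counts a child with two days of runny nose at Grade 1 the same as a child with a Grade 3 fever (102.5 to <104.9°F, SAP Appendix 3) or an otitis media that reached Grade 2 because a prescription was used (Appendix 2). Neither of the latter is a serious event unless it meets a criterion in Appendix 4, and neither is an LRI. Each enters a comparison with placebo only as a Grade 1+ event.

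If a live-attenuated vaccine made such illness worse without changing how many children had any, the planned contrast would be centred on zero. The reader would have a grade table by arm, but no estimate of the difference and no interval showing what is compatible with chance at about 40 children per arm.

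**Working it through.** **1. What is compared, by event type (SAP 3.1, 4.1.2, 4.2.1, Appendices 1 to 4)**

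| Event | Cut used in a comparison with placebo | Above that cut |
|---|---|---|
| LRI | Grade 1+ (as a solicited event) and Grade 2+ (own outcome) | Summarized; listed individually |
| Any event meeting a seriousness criterion | Serious, yes/no, to Day 56 | Summarized; listed individually |
| Fever, otitis media, URI, not serious | Grade 1+ only | Summarized |

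The gap is the last row.

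**2. Why the planned difference is zero there**

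Let a be the proportion with any solicited event of Grade 1+, and s the share of those whose worst grade is 2 or higher. The planned contrast is a(vaccine) − a(placebo). The Grade 2+ contrast is a·s(vaccine) − a·s(placebo). If a is equal in both arms, the first is zero whatever happens to s.

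**3. Inputs**

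- About 40 per arm (SAP 2.4); two-sided nominal 0.05 and Fisher's exact test (SAP 4.2.1).
- There is no plan figure to reproduce. The SAP gives no safety event rate, effect size or power, and it refers to protocol Section 9.3, which is not in the available text. All rates below are assumptions.

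**4. Rejection probability, 40 v 40, by exact enumeration**

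Power = Σ P(X=i)·P(Y=j) over all pairs (i, j) with Fisher p < 0.05, where X and Y are binomial with n = 40.

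| Assumed true rates, placebo v vaccine | Comparison | Rejection probability |
|---|---|---|
| 80% v 80% any event | Grade 1+ (planned) | 0.028 |
| 20% v 30% | Grade 2+ (added) | 0.12 |
| 20% v 40% | Grade 2+ (added) | 0.41 |
| 20% v 45% | Grade 2+ (added) | 0.59 |

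In a wider range with equal incidence (any event 40 to 80%; Grade 2+ share 10 to 20% on placebo and 50 to 70% on vaccine), the Grade 1+ test rejects 2.8 to 3.0% of the time, and Grade 2+ power runs from 24% (8% v 20%) to 99.8% (8% v 56%). The result depends almost wholly on the size of shift assumed.

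**5. Worked example (assumed counts)**

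- Any solicited event: 24/40 v 24/40, difference 0, Fisher p = 1.00.
- Same children, Grade 2+: 16/40 vaccine v 4/40 placebo. Difference = 0.40 − 0.10 = 0.30. Standard error = √(0.40×0.60/40 + 0.10×0.90/40) = 0.091. Simple 95% CI = 0.30 ± 1.96×0.091, or 12 to 48 points. Fisher p = 0.004.
- A rank-sum test on worst grade for these children (vaccine grades 0/1/2/3 = 16/8/12/4, placebo 16/20/3/1) gives p = 0.14.

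**6. Where the plan does see a shift**

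If LRIs moved from Grade 1 to Grade 2+, the planned Grade 2+ LRI comparison would register it: 5/40 v 0/40 gives p = 0.055, and 6/40 v 0/40 gives p = 0.026.

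**The case against.** A reader might infer that severity is not compared with placebo at all. The documents do not support that. Grade 2+ LRI and serious events are primary outcomes with the full set of comparisons. Outside fever, Grade 3 can involve hospitalization and Grade 4 requires it (Appendix 2), and inpatient hospitalization makes an event serious (Appendix 4).

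Nor would a shift be hidden. Worst grade per child, and severity by category and Preferred Term, will be in the report. Among the Go/No-Go criteria in Section 2.5, the monitoring board also looks at Grade 2+ LRI and at repeated Grade 4 events of similar type, otitis media and pharyngitis among them.

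It can also be said that the plan does not rest its safety judgement on these tests. Section 2.4 states that a full safety assessment needs much larger samples, and Section 4.1.4 urges caution over the many tests. Testing selected cuts and describing the rest is defensible in a Phase I/II trial of this size. The Analysis Implementation Plan and the protocol's statistical section, neither of which is available here, might say more.

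All of this stands, and it limits the point to non-serious fever, otitis media and URI. It does not remove it. The objective says compare, and Section 4.2.1 does not explain why grade is only described. For RSV-associated illness, by contrast, Section 4.3.2 says that no formal tests are planned and gives the reason.

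**Conclusion.** The point holds within that limit. For non-LRI, non-serious solicited events, a change in severity at equal incidence has a true difference of zero in the planned comparison and appears only in a descriptive table. The objective and Section 4.2.1 do not match on this part.

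The size is uncertain because the documents give no grade distribution. With 80% having any event in both arms, the planned test rejects about 3% of the time, against about 12% with a Grade 2+ comparison for 20% v 30%, and about 59% for 20% v 45%. It would be tempting to read this as a large loss of power. That follows only if Grade 2+ events about double or more, which nothing in the documents indicates. What is chiefly lost is the estimated difference and its interval. This is a cheap improvement, not a flaw that undermines the safety analysis.

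**What to change.** In SAP Section 4.2.1, after the sentence on worst grade, add: *The proportion of participants with a worst solicited AE of Grade 2 or higher, Days 0-28, will be compared between each vaccine arm and placebo using the same difference in proportions, 95% CI and Fisher's exact test as the primary safety outcomes.* Keep the Grade 1+ comparison unchanged.

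A rank-sum test on worst grade should not be added. It would rank a temperature scale (Appendix 3) together with a scale based on intervention and activity (Appendix 2). A code of 0 for no event would collide with fever Grade 0, which is a recorded reading. When incidence is unchanged it is also less sensitive than the Grade 2+ cut, as the worked example shows.

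If the sponsor prefers description only, the alternative is to reword the objective so that severity beyond the Grade 2+ LRI and serious-event outcomes is described, not compared.

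The cost is one sentence and a few table rows. Worst grade per child is already derived, so no new data are needed. The downside is one more nominal comparison per vaccine arm, which the caution in Section 4.1.4 already covers.

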#### 4.2.2 Analysis of the primary immunogenicity objectives

Children will be classified as a responder to the vaccine if they achieve a ≥4-fold increase in serum RSV-neutralizing antibody titers from pre-study product administration to the Day 56 Visit. Proportions (95% CIs) of responders will be summarized by arm. Each confidence interval will be assessed to determine if the upper limit is less than 70%. Differences between each vaccine arm and the placebo arm (which take into account background rates which could vary by season), as well as differences between each combination of vaccine arms, will be summarized with 95% CIs. Pair-wise differences in response rates between the vaccine arms (and differences between vaccine and placebo arms) will be assessed using two-tailed Fisher's exact tests with a nominal significance level of 0.05.

#### Sensitivity and secondary analyses of the primary immunogenicity objective

Sensitivity analysis will include:

(i) Repeat above-described analyses after replacing the selected child with other siblings or other children from the same household who enrolled on the same date.

Secondary analyses will include:

- (i) Repeat above-described analyses with participants missing their Day 56 antibody titer reclassified as failures.
- (ii) Repeat above-described analyses using an intent-to-treat population that includes all participants as-randomized regardless of vaccine receipt.
- (iii) Repeat above-described analyses using an outcome measure defined as a ≥4-fold increase in serum RSV-neutralizing antibody titers from pre-study product administration to the Day 56 Visit and no wild-type RSV infection detected before Day 56.

(iv) To examine seasonal effects and account for potential ascertainment differences related to COVID-19, response rates for each arm and differences in proportions between each arm will be summarized by calendar year of enrollment. A Breslow-Day test with a nominal significance level of 0.05 will be used to test for homogeneity in the vaccine effect by calendar year for each comparison between arms. Unless the Breslow-Day test indicates there is not homogeneity in vaccine effect by calendar year, a strata-adjusted difference in proportions will be summarized using a Cochran-Mantel-Haenszel method with 95% Klingenberg (2014) confidence limits.

# 4.3 Analysis Approaches (Secondary Objectives)

#### 4.3.1 Secondary immunogenicity up to Day 56

The proportion of participants achieving ≥4-fold increases in serum RSV F IgG titers from pre-study product administration to Day 56 will be summarized using the same methods as for the primary initial response to vaccine immunogenicity outcome measured by serum RSV-neutralizing antibodies.

Titers of serum RSV-neutralizing antibodies and RSV F IgG will be summarized at pre-study product administration and the Day 56 visit. Changes from the pre-study product administration to Day 56 will also be summarized. Levels and changes will be compared between time points using Wilcoxon signed-rank tests and between arms using pair-wise Wilcoxon rank sum tests. Titers will be analyzed on the reciprocal log2 scale. Sensitivity analyses will be performed by replacing the selected child with other siblings or other children from the same household who enrolled on the same date. If enrollment extends over more than one season, response rates will be summarized by calendar year of enrollment to examine seasonal effects.

Titers below the lower limit of detection or above the upper limit of detection will be assigned a value equal to the corresponding limit of detection.

#### 4.3.2 RSV medically-attended illness during RSV surveillance

Numbers and proportions (with 95% CIs) of participants experiencing RSV-associated medically attended acute respiratory illness (RSV-MAARI) and RSV-associated acute lower respiratory illness (RSV-MAALRI) will be summarized by arm. In addition, the worst graded event experienced by a participant (if a participant experiences more than one illness during the season) will be summarized. Since the number of these events is expected to be small, no formal statistical comparison tests are planned.

If RSV-MAARI or RSV-MAALRI events occur during the RSV surveillance period but prior to Day 56, they will be included in analyses corresponding to this objective.

Participants who receive the following treatments will be excluded from analyses, unless they experienced an RSV-associated medically attended illness prior to receiving treatment:

- systemic corticosteroids for more than 14 days at a dosage equivalent to prednisone at >2 mg/kg or 20 mg daily or other immune-modifying drugs;
- immunoglobulins and/or any blood products;

anti-RSV products (such as ribavirin or RSV IG or RSV mAb).

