#### 2.4 Overview of Sample Size Considerations

The target sample size of approximately 40 per arm was chosen to gather more data on safety and to yield sufficiently precise confidence intervals around Day 56 immunogenicity to help inform which candidate vaccines should go forward into larger studies. The total expected sample size is approximately 130, including approximately 40 each in the placebo and two candidate vaccine arms that remain open under protocol V2.0 (RSV ΔNS2/Δ1313/I1314L, RSV 6120/ΔNS2/1030s), as well as all participants previously randomized to receive RSV 276 under protocol V1.0 prior to closure of this arm.

To fully assess safety, much larger sample sizes will be required, and additional studies will need to be conducted on the candidate vaccines identified as promising in this trial. Declaring superiority in immunogenicity of one vaccine candidate over another will only be possible if one candidate has very poor immunogenicity. Additional details regarding sample size considerations are included in Section 9.3 of the protocol.

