#### 3.2 **Secondary Outcome Measures**

Immunogenicity Outcome measure [Secondary Objective 1]:

≥4-fold rise in serum RSV F IgG from pre-study product administration (screening) to the Day 56 Visit

Immunogenicity Outcome measures [Secondary Objective 2]:

- Titer of serum RSV F IgG at the Day 56 Visit
- Titer of serum RSV-neutralizing antibodies at the Day 56 Visit

Safety Outcome measures [Secondary Objective 3]:

- RSV-MAARI and maximum grade (if more than one illness within a participant)
- RSV-MAALRI and maximum grade (if more than one illness within a participant)

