# 4 Statistical Principles

#### 4.1 General Considerations

#### 4.1.1 Analysis populations

- Any participants found to be ineligible will be included in screening, accrual and eligibility summaries only.
- Safety population: All children (regardless of the number of children enrolled in a given household on the same date) who receive study product will be included in safety analyses. Safety outcome measures will be included if they occur after study product administration.
- Immunogenicity population: Children who received study vaccine and who have available data
  regarding outcome measures at screening and Day 56. If more than one child from a
  household is enrolled on the same date, one participant will be randomly selected to be
  included in the primary analysis.
  - Participants who have received the following treatments prior to the Day 56 visit will be excluded from the immunogenicity population (See Section 5.11.2 of the protocol for additional details):
    - systemic corticosteroids for more than 14 days at a dosage equivalent to prednisone at >2 mg/kg or 20 mg daily or other immune-modifying drugs;
    - immunoglobulins and/or any blood products;
    - anti-RSV products (such as ribavirin or RSV IG or RSV mAb).

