### 4.5 Analysis Approaches (Virology)

At each Illness Visit, a respiratory viral sample will be collected (i.e., nasal wash or nasal swab) to evaluate for the presence of RSV and other respiratory pathogens (adventitious agents). Note: Under protocol version 1.0, nasal wash samples were collected from participants. Under protocol version 2.0, the collection has been changed to nasal swab samples to decrease potential exposure of study staff to SARS-CoV-2 and allow parents/guardians to collect samples, if possible and feasible for parents/guardians. During each study period (Acute Phase, Post-Acute Phase, and RSV Season Surveillance), more than one nasal wash/swab might be performed. The overall number and proportion of children with at least one Illness Visit nasal wash/swab will be calculated for each vaccine arm by study period. Frequencies will also be calculated for each calendar year and collection method (caretaker versus medical personnel).

Among those with respiratory viral sample test results, the number and proportion with each observed combination of vaccine virus RSV, wt-RSV, and other adventitious agents will be calculated by study period and by arm. Among all children, the number and proportion with an Illness Visit where RSV virus (wt or vaccine virus) was detected (with or without other adventitious agents detected) will also be calculated for each vaccine arm by study period. Frequencies will also be calculated for each calendar year and collection method (caretaker versus medical personnel).

Participants who receive the following treatments will be excluded from analyses, unless they experienced an illness visit prior to receiving treatment:

- systemic corticosteroids for more than 14 days at a dosage equivalent to prednisone at >2 mg/kg or 20 mg daily or other immune-modifying drugs;
- immunoglobulins and/or any blood products;
- anti-RSV products (such as ribavirin or RSV IG or RSV mAb).

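### SAP 4.3.2 and 4.5 drop treated children only when no event came first, so the denominator depends on the outcome; in 4.3.2 this also conflicts with the safety population in 4.1.1

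*SAP*

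**What the plan says.** SAP Section 4.3.2 reports the number and proportion of children with RSV-MAARI and RSV-MAALRI by arm, with 95% CIs, plus the worst grade per child. It then sets the rule: "Participants who receive the following treatments will be excluded from analyses, unless they experienced an RSV-associated medically attended illness prior to receiving treatment". The listed treatments are long-course systemic steroids or other immune modifiers, immunoglobulin or blood products, and anti-RSV products. The section is descriptive: "Since the number of these events is expected to be small, no formal statistical comparison tests are planned".

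SAP Section 4.5 (virology) repeats the rule with a different retention condition: "Participants who receive the following treatments will be excluded from analyses, unless they experienced an illness visit prior to receiving treatment". One of the results it governs is this: "The overall number and proportion of children with at least one Illness Visit nasal wash/swab will be calculated for each vaccine arm by study period".

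SAP Section 4.1.1 defines the safety population as all children "who receive study product will be included in safety analyses". It lists the same treatments as exclusions for the immunogenicity population only, and there limits them to treatment before the Day 56 visit. Sections 4.3.2 and 4.5 set no time limit. SAP Sections 2.3.2 and 3.2 label RSV-MAARI and RSV-MAALRI as safety outcomes.

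**The concern.** A treated child stays in the 4.3.2 analysis only if an RSV illness came before the treatment. A treated child without one disappears, along with the event-free weeks before treatment and any RSV illness, and its grade, afterwards. This is selection on the outcome, and it applies to a simple proportion that makes no use of follow-up time.

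Because there is no time limit, a treatment in March removes a child from a summary of November to March. In 4.5, a late treatment also removes a child with no earlier illness visit from the Acute and Post-Acute summaries, although those periods ended before the treatment.

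At stake is the reading of Secondary Objective 3, which is to describe and compare the frequency and severity of RSV illness across arms. With few events expected, one discarded illness is visible in the result. The sensitivity analyses listed in the SAP (Sections 4.2.2 and 4.3.1) concern immunogenicity. No analysis of RSV illness with all children kept, or censored at treatment, is described, so a reader could not see the effect of the rule.

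**Working it through.** The documents state no event rate, treatment rate or precision for this analysis, so there is no figure of the plan's to reproduce. The only numerical input from the documents is the arm size in SAP Section 2.4: "The target sample size of approximately 40 per arm was chosen to gather more data on safety". Event risks, treatment rates and hazard ratios below are assumptions.

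**1. Counting, n = 40.** Let e be the events counted under the rule, k the treated children dropped, and m the number of those k who have an RSV illness after treatment.

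- Rule: e/(40 − k). All dosed children, all events: (e + m)/40.
- With e = 4 and m = 0, all children give 4/40 = 10.0% (Clopper-Pearson 95% CI 2.8% to 23.7%, width 20.9 points).

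| k dropped | Rule | Relative excess k/(40 − k) |
|---|---|---|
| 0 | 4/40 = 10.0% | 0 |
| 1 | 4/39 = 10.3% | 2.6% |
| 2 | 4/38 = 10.5% | 5.3% |
| 4 | 4/36 = 11.1% (CI 3.1% to 26.1%) | 11.1% |

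- Direction: e/(40 − k) < (e + m)/40 exactly when m/k > e/(40 − k). The rule understates whenever the share of dropped children who later fall ill exceeds the reported proportion. With e = 4, k = 4 and m = 1, the rule gives 11.1% and the full count gives 5/40 = 12.5%.

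**2. Treatment arising during the season.** Take constant hazards a (event) and b (treatment) over one season, with a = −ln(1 − risk) and b = −ln(1 − treated).

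- P(event first) = [a/(a + b)] × [1 − e^−(a+b)]; P(neither) = e^−(a+b).
- Rule = P(event first) / [P(event first) + P(neither)].
- At 10% risk and 10% treated, a = b = 0.105, so P(event first) = 0.5 × (1 − 0.81) = 0.095 and the rule gives 0.095/(0.095 + 0.81) = 10.5%.
- At 10% risk with 2%, 5%, 10% and 25% treated, the rule gives 10.1%, 10.2%, 10.5% and 11.4%. The true value is 10.0% when treatment neither predicts nor changes risk.
- If the hazard after treatment is multiplied by h, all-children risk = 1 − e^−(a+b) − b·e^−ha·[1 − e^−(a+b−ha)]/(a + b − ha). At 10% treated this is 10.9% for h = 3 and 12.0% for h = 6, against 10.5% under the rule (relative −4% and −13%). At 25% treated it is 12.3% and 15.2%, against 11.4% (−7% and −25%).
- For h = 0.2 (a protective treatment), the relative bias is upward, from +2% (2% treated) to +27% (25% treated).

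**3. Treatment at the start of the season.** The rule then returns the risk of the untreated. With equal risk there is no bias (10.0% in both). If 10% of the arm is treated and has 30% risk, the rule gives 10.0%, while all children give 0.9 × 10% + 0.1 × 30% = 12.0%.

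**4. Arm contrast.** With true risks of 20% and 10%, no treatment effect and 10% treated in both arms, the rule gives a difference of 10.4 points (true 10.0) and a ratio of 0.502 (true 0.500). With 25% treated, the figures are 11.1 points and 0.507.

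**5. Sections set side by side.** Section 4.1.1 includes every dosed child in safety analyses. Sections 2.3.2 and 3.2 call RSV-MAARI and RSV-MAALRI safety outcomes. Section 4.3.2 removes some dosed children from them. As written, these cannot all hold.

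**The case against.** The strongest reply has four parts.

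- **The analysis is descriptive and secondary.** It carries no formal test and feeds no primary outcome and no Go/No-Go criterion. This stands, and it limits the severity.
- **Treatment use is probably low.** Participants are healthy children aged 6 to under 25 months, and Protocol Section 5.11.2 asks that the listed treatments be avoided unless clinically indicated. This also stands. Use is not ruled out, however: Protocol Section 4.2.6 bars planned anti-RSV products only up to day 56, while surveillance runs to 31 March.
- **The retention clause has a purpose.** Without it, a child treated because of RSV illness would lose that illness. True, but keeping every dosed child protects those events too.
- **Section 4.3.2 is a specific exception to a general rule, aimed at confounding by treatment.** Section 4.1.1 does not signal such an exception for safety, though it spells one out for immunogenicity. Protocol Section 5.11.2 gives immunogenicity as its reason for avoiding these treatments. If RSV illness in the absence of treatment is the target, censoring uses the follow-up before treatment; deletion discards it.

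A reader might infer that every proportion is biased upward. The documents do not support that. Illness after treatment is discarded too, which can turn the bias downward. A child with an earlier RSV-MAARI that was not lower respiratory stays in as an RSV-MAALRI non-event. In 4.5, any earlier illness visit in any period keeps a child in, possibly as a non-event later. The virology combination shares are taken among children with test results and sum to 100%, so they cannot all rise.

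Nor are these the only safety data on disease severity. Grade 2 or higher LRIs to Day 28 and serious AEs to Day 56 use all dosed children, and Protocol Section 7.2 follows serious AEs with onset during RSV surveillance.

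**Conclusion.** The concern holds for the structure of the rule. In 4.3.2, and secondarily in 4.5, inclusion of a treated child depends on whether an event has already occurred, and 4.3.2 must be reconciled with 4.1.1.

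The direction is not fixed. RSV-MAARI proportions tend to be too high when treatment falls within the season and treated children are not at higher later risk. They can be too low when those children are at higher risk. There is no bias if nobody is treated, or if treatment precedes the season and is unrelated to risk.

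The likely size is small: 0.3 to 1.1 points at 4 events in 40 with 1 to 4 event-free children dropped, against an interval about 21 points wide. That rests on assumed counts. A large distortion of the arm comparison would need heavy or unequal treatment use, and nothing in the documents of this randomized, double-blind trial points to either. The change should be made before analysis, but it does not threaten the trial's primary conclusions.

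**What to change.** - **Section 4.3.2:** delete the exclusion rule. Make the main summary all children who received study product, with all RSV-MAARI and RSV-MAALRI events and grades counted whatever treatment followed or preceded them. This agrees with 4.1.1.
- **Reporting:** give the number of children receiving a listed treatment by arm, with timing relative to the season and to any RSV illness.
- **Optional support:** a Kaplan-Meier estimate by arm censored at first listed treatment, with a note that such censoring may be informative and that few events in about 40 children per arm limit what it can add.
- **Section 4.5:** likewise keep all children. At minimum, do not remove data collected before the treatment, so that completed study periods stay intact.

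The cost is SAP wording and slightly more programming. Protocol Section 7.2 already requires these medications in the eCRF throughout the study, and the present rule already depends on their timing, so no new data are needed.
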